#### **6.5.4.4 Immune-related adverse events**

AEs associated with pembrolizumab exposure may represent an immunologic etiology. These irAEs may occur shortly after the first dose or several months after the last dose of pembrolizumab treatment and may affect more than one body system simultaneously. Immune-related AEs are thought to be caused by unrestrained cellular immune responses directed at the normal host tissues. Therefore, early recognition and initiation of treatment is critical to reduce complications. Based on existing pembrolizumab clinical study data, most irAEs were reversible and could be managed with interruptions of pembrolizumab, administration of corticosteroids and/or other supportive care.

Investigators must be extremely vigilant and be ready to intervene early in the management of irAEs because the onset of symptoms of irAEs (eg, pneumonitis) may be subtle. For suspected irAEs, adequate evaluation should be performed to confirm etiology or exclude neoplastic, infectious, metabolic, toxin, or other etiologic causes. Additional procedures or tests such as bronchoscopy, endoscopy, skin biopsy may be included as part of the evaluation. Based on the severity of irAEs, withhold or permanently discontinue pembrolizumab and/or SAR444245 and/or cetuximab and administer corticosteroids.

SAR444245 may increase the incidence and severity of these events.

Dose modification and toxicity management guidelines for irAEs are provided in [Table 10](#). Of note, if the AE is considered immune-related, both drugs in the combination should be held according to recommended dose modifications. If a participant experiences several irAEs, the most conservative recommendation should be followed.

When pembrolizumab can be restarted, it should be administered at the initial planned dose and schedule as no modification is allowed:

- If the toxicity does not resolve or the criteria for resuming treatment are not met, the participant must be discontinued from all study drugs.
- If the toxicities do resolve and conditions are aligned with what is defined in [Table 10](#), the combination of SAR444245, pembrolizumab and cetuximab may be restarted at the discretion of the Investigator. In these cases where the toxicity is attributed to the combination or to SAR444245 alone, re-initiation of pembrolizumab as a monotherapy may be considered after communication with the Sponsor.

**Table 10 - Dose modification and toxicity management guidelines for immune-related AEs associated with pembrolizumab and SAR444245**

General instructions:

1. Treat severe and life-threatening irAEs with IV corticosteroids followed by oral steroids. Begin other immunosuppressive treatment if the irAEs are not controlled by corticosteroids.
2. Pembrolizumab and SAR444245 must be permanently discontinued if the irAE does not resolve or the corticosteroid dose is not  $\leq 10$  mg/day within 12 weeks of the last pembrolizumab treatment.
3. Begin the corticosteroid taper when the irAE is  $\leq$  Grade 1 and continue at least 4 weeks.
4. If pembrolizumab and SAR444245 have been withheld, pembrolizumab and SAR444245 may be resumed after the irAE decreased to  $\leq$  Grade 1 after corticosteroid taper.

| irAEs                                       | Toxicity grade (CTCAE V5.0)            | Action with pembrolizumab and SAR444245 | Corticosteroid and/or other therapies  | Monitoring and follow-up  |
|---|--|---|--|---|
| Pneumonitis                                 | Grade 2                                | Withhold a                   | Administer corticosteroids (initial dose of 1 to 2 mg/kg prednisone or equivalent) followed by taper.
Add prophylactic antibiotics for opportunistic infections.  | Monitor participants for signs and symptoms of pneumonitis.
Evaluate participants with suspected pneumonitis with radiographic imaging and initiate corticosteroid treatment.  |
|   | Recurrent Grade 2, Grade 3 or 4        | Permanently discontinue b    |  |   |
| Diarrhea/Colitis                            | Grade 2 or 3                           | Withhold a                   | Administer corticosteroids (initial dose of 1 to 2 mg/kg prednisone or equivalent) followed by taper.  | Monitor participants for signs and symptoms of enterocolitis (ie, diarrhea, abdominal pain, blood or mucus in stool with or without fever) and of bowel perforation (ie, peritoneal signs and ileus).
Participants with $\geq$ Grade 2 diarrhea suspecting colitis should consider GI consultation and performing endoscopy to rule out colitis.
Participants with diarrhea/colitis should be advised to drink liberal quantities of clear fluids. If sufficient oral fluid intake is not feasible, fluid and electrolytes should be substituted via IV infusion. |
|   | Recurrent Grade 3 or Grade 4           | Permanently discontinue b    |  |   |
| AST or ALT elevation or Increased Bilirubin | Grade 2 c                   | Withhold a                   | Administer corticosteroids (initial dose of 0.5 to 1 mg/kg prednisone or equivalent) followed by taper.
Administer corticosteroids (initial dose of 1 to 2 mg/kg prednisone or equivalent) followed by taper. | Monitor with liver function tests (consider weekly or more frequently until liver enzyme value returned to baseline or is stable).  |
|   | Grade 3 d or 4 e | Permanently discontinue b    |  |   |

| irAEs  | Toxicity grade (CTCAE V5.0)   | Action with pembrolizumab and SAR444245                  | Corticosteroid and/or other therapies  | Monitoring and follow-up   |
|---|--|---|---|---|
| Type 1 Diabetes Mellitus (T1DM) or Hyperglycemia                            | New onset T1DM or Grade 3 or 4 hyperglycemia associated with evidence of $\beta$ -cell failure | Withhold a,f   | Initiate insulin replacement therapy for participants with T1DM. Administer antihyperglycemic in participants with hyperglycemia. | Monitor participants for hyperglycemia or other signs and symptoms of diabetes.                       |
| Hypophysitis  | Grade 2  | Withhold a   | Administer corticosteroids and initiate hormonal replacements as clinically indicated.  | Monitor for signs and symptoms of hypophysitis (including hypopituitarism and adrenal insufficiency). |
|   | Grade 3 or 4   | Withhold a or permanently discontinue b,f |   |   |
| Hyperthyroidism   | Grade 2  | Continue  | Treat with nonselective beta-blockers (eg, propranolol) or thionamides as appropriate.  | Monitor for signs and symptoms of thyroid disorders.  |
|   | Grade 3 or 4   | Withhold a or permanently discontinue b,f |   |   |
| Hypothyroidism  | Grade 2, 3, or 4   | Continue  | Initiate thyroid replacement hormones (eg, levothyroxine or liothyronine) per SOC   | Monitor for signs and symptoms of thyroid disorders.  |
| Nephritis: grading according to increased creatinine or acute kidney injury | Grade 2  | Withhold a   | Administer corticosteroids (prednisone 1 to 2 mg/kg or equivalent) followed by taper.   | Monitor changes of renal function.  |
|   | Grade 3 or 4   | Permanently discontinue b                            |   |   |
| Neurological Toxicities   | Grade 2  | Withhold a   | Based on severity of AE administer corticosteroids  | Ensure adequate evaluation to confirm etiology and/or exclude other causes                            |
|   | Grade 3 or 4   | Permanently discontinue b                            |   |   |
| Myocarditis   | Grade 2, 3 or 4  | Permanently discontinue b                            | Based on severity of AE administer corticosteroids.   | Ensure adequate evaluation to confirm etiology and/or exclude other causes.                           |
| Exfoliative Dermatologic Conditions   | Suspected SJS, TEN, or DRESS   | Withhold a   | Based on severity of AE administer corticosteroids  | Ensure adequate evaluation to confirm etiology and/or exclude other causes                            |
|   | Confirmed SJS, TEN, or DRESS   | Permanently discontinue b                            |   |   |

| irAEs           | Toxicity grade (CTCAE V5.0)  | Action with pembrolizumab and SAR444245                              | Corticosteroid and/or other therapies               | Monitoring and follow-up  |
|-----------------|------------------------------|--|---|---|
| All Other irAEs | Persistent Grade 2           | Withhold a  | Based on severity of AE administer corticosteroids. | Ensure adequate evaluation to confirm etiology or exclude other causes. |
|                 | Grade 3                      | Withhold a or discontinue based on the event g |   |   |
|                 | Recurrent Grade 3 or Grade 4 | Permanently discontinue b                                 |   |   |

a SAR444245 to be withheld plus pembrolizumab: to be withheld corresponds to “cycle delay”.

b Permanently discontinuation of full study treatment.

c AST/ALT: >3.0 to 5.0 x ULN if baseline normal; >3.0 to 5.0 x baseline, if baseline abnormal; bilirubin:>1.5 to 3.0 x ULN if baseline normal; >1.5 to 3.0 x baseline if baseline abnormal.

d AST/ALT: >5.0 to 20.0 x ULN, if baseline normal; >5.0 to 20.0 x baseline, if baseline abnormal; bilirubin:>3.0 to 10.0 x ULN if baseline normal; >3.0 to 10.0 x baseline if baseline abnormal.

e AST/ALT: >20.0 x ULN, if baseline normal; >20.0 x baseline, if baseline abnormal; bilirubin: >10.0 x ULN if baseline normal; >10.0 x baseline if baseline abnormal.

f The decision to withhold or permanently discontinue pembrolizumab and SAR444245 is at the discretion of the investigator or treating physician. If control achieved or ≤Grade 2, pembrolizumab and SAR444245 may be resumed.

g Events that require discontinuation include but are not limited to: encephalitis and other clinically important irAEs (eg. vasculitis and sclerosing cholangitis).

AE(s)=adverse event(s); ALT= alanine aminotransferase; AST=aspartate aminotransferase; CTCAE=Common Terminology Criteria for Adverse Events; DRESS=Drug Rash with Eosinophilia and Systemic Symptom; GI=gastrointestinal; IO=immuno-oncology; ir=immune related; IV=intravenous; SJS=Stevens-Johnson Syndrome; T1DM=type 1 diabetes mellitus; TEN=Toxic Epidermal Necrolysis; ULN=upper limit of normal. Note: Non-irAE will be managed as appropriate, following clinical practice recommendations.

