#### 6.1.1 Investigational medicinal product

Investigational medicinal product (IMP) is defined as SAR444245, cetuximab and pembrolizumab administered as described in [Section 4.1](#). Details of each IMP component to be administered are shown in [Table 4](#).

Preparation and administration of IMP are detailed in the pharmacy manual. Hydration is required for SAR444245 infusions. Details are provided in Section 6.1.3 of the master protocol.

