### **6.5 DOSE MODIFICATION**

#### **6.5.1 General rules**

Dose modifications for SAR444245 is permitted according to the guidelines described in this section. Pembrolizumab dose reductions are not permitted. Pembrolizumab treatment may be interrupted or discontinued due to toxicity. Dose modifications for cetuximab are permitted, and modification of dose levels in case of dose reduction is described in [Table 5](#).

Dose modifications different from those stated in the protocol should only be made in consultation with the Sponsor, unless required for immediate participant safety.

**Cycle delay** (ie, Day 1 should be delayed for all IMPs) or **dose omission** (ie, omission of any component of the IMP within a cycle) are permitted in case of treatment-emergent adverse event (TEAE). Dose modification will be made according to the worst grade of toxicity observed within a cycle. If a participant experiences several toxicities and there are conflicting recommendations, the most conservative recommended dose adjustment should be followed. Once a dose has been decreased, intra-patient re-escalation back to the previous dose level is not permitted.

Administration of the study treatment will be discontinued in the event of a TEAE that persists despite appropriate dose modifications or any other TEAE that, in the opinion of the Investigator, warrants discontinuation.

If any of the IMP components is permanently discontinued, the other IMP component can be continued until disease progression or other criteria as detailed in Section 7.1.1 of the master protocol are met. In this case it is partial permanent discontinuation and the end-of-treatment (EOT) assessment will be 30 days after the date of the last administration of the remaining IMP(s). When all IMP components are permanently discontinued it is full permanent discontinuation.

All changes to study treatment administration must be recorded in the electronic case report form (e-CRF).

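### Cohort A2: the immune-related adverse event rules do not agree on whether cetuximab is held or stopped along with the other two drugs

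*Protocol*

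**What the plan says.** All references are to the Cohort A2 substudy protocol unless stated otherwise.

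Section 6.1.1 fixes the regimen: "Investigational medicinal product (IMP) is defined as SAR444245, cetuximab and pembrolizumab".

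Section 6.5.4.4 makes four statements about an irAE:
- Depending on severity, "withhold or permanently discontinue pembrolizumab and/or SAR444245 and/or cetuximab and administer corticosteroids".
- If the event is considered immune-related, "both drugs in the combination should be held according to recommended dose modifications".
- If it does not resolve, or the criteria for resuming are not met, "the participant must be discontinued from all study drugs".
- If it resolves in line with Table 10, "the combination of SAR444245, pembrolizumab and cetuximab may be restarted at the discretion of the Investigator".

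In Table 10 the action column is headed for pembrolizumab and SAR444245. General instruction 2 reads in part "Pembrolizumab and SAR444245 must be permanently discontinued if the irAE does not resolve", and general instruction 4 describes resuming the same two drugs. Footnote a equates withholding those two with a cycle delay. Footnote b explains a permanent stop as "Permanently discontinuation of full study treatment". Footnote f again refers to pembrolizumab and SAR444245.

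Section 6.5.1 defines a cycle delay as postponing Day 1 for every IMP, and treats leaving out a component within a cycle separately, as a dose omission. It also contains a general permission: "If any of the IMP components is permanently discontinued, the other IMP component can be continued until disease progression", or until other criteria in the master protocol are met.

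**The concern.** A site managing an irAE in this cohort has to decide about cetuximab, which is given weekly. If the irAE arises early in a cycle, cetuximab is the next drug due. The text it would consult gives more than one answer.

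Cetuximab is continued until progression and is active alone: the B2 substudy, Section 2.2.3.1, cites a 13% response rate for monotherapy after platinum failure (a different population from A2). If some participants keep cetuximab after an irAE and others do not, because sites followed different sentences, the A2 objective response rate describes a mixture of regimens that the protocol did not intend to leave open. The same ambiguity affects the end-of-treatment date and, in the safety run-in, whether a participant counts as having a DLT.

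**Working it through.** The point rests on wording, so the passages are set side by side. The only arithmetic concerns the DLT window.

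**Hold: is cetuximab included?**
- Section 6.5.4.4, severity sentence: optional (and/or).
- Section 6.5.4.4, hold sentence: two unnamed drugs out of three.
- Table 10, column heading and instruction 4: two named drugs; cetuximab not mentioned.
- Table 10, footnote a, read with the definition in Section 6.5.1: a cycle delay, hence all three, but defined by Day 1.
- Section 6.5.4.4, restart bullet: all three restarted, which presumes cetuximab had been interrupted.
- Day 8 and Day 15 cetuximab: addressed by none of these. Sections 6.5.1 and 6.5.2 treat them as omissions, not as part of a cycle delay.

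**Permanent stop: is cetuximab included?**
- Section 6.5.4.4, unresolved toxicity: yes, all study drugs.
- Table 10, footnote b: yes, full study treatment.
- Table 10, instruction 2, for an irAE that does not resolve: two drugs named.
- Table 10, column heading and footnote f: two drugs named.
- Grade 3 or 4 hypophysitis and hyperthyroidism: the permanent-stop option carries footnotes b and f together, so one cell points both to full treatment and to two drugs.

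**End-of-treatment date.** Under Section 6.5.1 the assessment after a partial discontinuation falls 30 days after the last dose of whatever remains. If cetuximab continues for k weeks after the other two stop, the date moves later by 7 × k days.

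**DLT counting in the safety run-in.**
1. The window is the 21 days of Cycle 1 (Section 4.1). SAR444245 and pembrolizumab are next due on Cycle 2 Day 1, which is 21 days after Day 1, study day 22. Cetuximab is due on Days 8 and 15.
2. Take a Grade 2 irAE with onset before the Day 8 dose, in a row where Table 10 says to withhold (for example pneumonitis or nephritis), and which meets no other DLT criterion.
3. If only pembrolizumab and SAR444245 are held, no dose is missed inside the window: 0 missed cetuximab doses, no DLT on this ground.
4. If cetuximab is held on both days, 2 doses are missed through toxicity. Section 4.1 counts more than one such missed dose as a DLT, and 2 > 1.
5. In Table 3, with 6 evaluable participants, 2 DLTs give S and 3 give D. One reclassified participant can therefore change the recommendation.

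**The case against.** The strongest reply is that the section can be read coherently. Section 6.5.4.4 names cetuximab twice in wording specific to the triplet, so it was adapted for A2. Table 10 is titled for irAEs associated with pembrolizumab and SAR444245, so its heading and instruction 2 naturally name those two; neither says that cetuximab continues. Footnote b defines the permanent-stop entries, and rows carrying b alone (pneumonitis, nephritis and myocarditis among them) have an explicit answer consistent with the text. Section 6.5.3 also leaves the final decision to the Investigator's judgement.

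Much of this stands, and it rules out several stronger readings that a reader might infer:
- That Table 10 orders cetuximab to continue. Instruction 2 does not mention cetuximab; it does not exclude it.
- That every permanent-stop row is undefined. Footnote b settles its scope where it stands alone.
- That Section 6.5.1 directly contradicts Section 6.5.4.4. It is a general permission, limited by master-protocol criteria that are not in the material reviewed.
- That DLT counts differ because a toxicity requiring permanent discontinuation of study drug is a DLT. That criterion is met as soon as pembrolizumab and SAR444245 stop, whatever happens to cetuximab.
- That the A2 rules were simply copied from a doublet. The hold sentence is identical to the one in the B1 substudy, where two drugs is correct, but carry-over is an inference and other parts of the section were adapted.

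What the reply does not answer is the hold. Footnote a leads to all three drugs under a two-drug heading, and no sentence covers Days 8 and 15. Nor does it explain why instruction 2 and the text differ in scope for the same event, or why two cells carry both b and f. The instruction to follow the most conservative recommendation applies to several toxicities or several irAEs, not to conflicting rules for one event.

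**Conclusion.** The inconsistency is real and should be corrected. It is clearest for holds. For permanent stops it is confined to instruction 2, the column heading, footnote f and the two cells that carry both footnotes.

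Its size cannot be given as a rate, because the protocol states no irAE frequency for the triplet; no effect on the response rate is estimated here. What can be said is that it applies to irAEs leading to a hold, or falling under the mismatched stop wording, among the approximately 40 participants, and that the readings differ by whether weekly cetuximab is given during the hold or after the stop.

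The DLT consequence assumes an irAE early in Cycle 1, not otherwise a DLT, with both the Day 8 and Day 15 doses missed. It matters for a run-in of 6 to 10 participants, although Table 3 guides the Study Board and does not bind it. Which rule is clinically right is not judged here.

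**What to change.** Reconcile Section 6.5.4.4 with Table 10 (column heading, general instructions 2 and 4, footnotes a, b and f), and cross-check the result against Section 6.5.1. Each irAE hold, stop and restart action should name SAR444245, pembrolizumab and cetuximab, and should say whether the Day 8 and Day 15 cetuximab doses are covered. The sponsor's clinical team decides the content.

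The cost is a wording change in one substudy. Sample size, endpoints and the planned analyses are unaffected.

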#### 6.5.4.5 Dermatologic toxicity

Cetuximab can cause dermatologic toxicities, including acneiform rash, skin drying and fissuring, paronychia inflammation, infectious sequelae (for example, *S. aureus* sepsis, abscess formation, cellulitis, blepharitis, conjunctivitis, keratitis/ulcerative keratitis with decreased visual acuity, cheilitis), and hypertrichosis.

The dosing of cetuximab will be omitted 1 to 2 weeks in the case of severe (Grade 3 or 4) acneiform rash. If acneiform rash improves during this time, then the dose of cetuximab should be reduced as indicated in Table 11. The dose modification guidelines in Table 5 should be followed for dermatologic toxicities other than acneiform rash.

If acneiform rash does not improve during this time, cetuximab will be permanently discontinued.

Participants who have omitted cetuximab therapy for more than 2 consecutive infusions due to acneiform rash, and upon resolution of the toxicity are still felt to be benefiting from cetuximab treatment may resume cetuximab with Sponsor approval.

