### ***Cetuximab***

- **Formulation:**
  - a clear, colorless solution for injection provided as 100 mg/50 mL (2 mg/mL) or 200 mg/100 mL in a single-dose vial
  - or*
  - 100 mg/20 mL or 500 mg/100 mL
  - or*
  - any other cetuximab formulation approved locally.
- **Route of administration:** IV infusion.
- **Dose regimen:** cetuximab will be given on Cycle 1 Day 1 as an initial loading dose of 400 mg/m^2 infused over 120 minutes (maximum infusion rate 10 mg/min or as per local practice and labels) followed by weekly 250 mg/m^2 infused over 60 minutes (maximum infusion rate 10 mg/min) for all subsequent doses starting with the Cycle 1 Day 8 administration, **until progressive disease (PD).**

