**Table 11 - Cetuximab dose modification for dermatologic toxicities**

| Dermatologic toxicities and infectious sequelae (eg, acneiform rash, mucocutaneous disease) | Recommended IMP dose modification  |
|--|---|
| 1st occurrence; Grade 3 or 4   | Day 1 of cycle: delay cycle until condition improves
Within cycle: Omit infusion 1 to 2 weeks; if condition improves, continue at the same dose of 250 mg/m^2. If no improvement, discontinue cetuximab. |
| 2nd occurrence; Grade 3 or 4   | Day 1 of cycle: delay cycle until condition improves
Within cycle: Omit infusion 1 to 2 weeks; if condition improves, permanently reduce at dose level 1. If no improvement, discontinue cetuximab.                              |
| 3rd occurrence; Grade 3 or 4   | Day 1 of cycle: delay cycle until condition improves
Within cycle: Omit infusion 1 to 2 weeks; if condition improves, permanently reduce at dose level 2. If no improvement, discontinue cetuximab.                              |
| 4th occurrence; Grade 3 or 4   | Permanently discontinue cetuximab.  |

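### Cohorts A2 and B2: the cetuximab rules for severe skin toxicity disagree on dose at first occurrence, on the governing table, and on when stopping or resumption applies

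*Protocol*

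**What the plan says.** **Cohort A2, Section 6.5.4.5 (text).** The section starts from a pause in dosing: "The dosing of cetuximab will be omitted 1 to 2 weeks in the case of severe (Grade 3 or 4) acneiform rash". It then gives four instructions:

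- After improvement: "If acneiform rash improves during this time, then the dose of cetuximab should be reduced as indicated in Table 11".
- For other skin events: "The dose modification guidelines in Table 5 should be followed for dermatologic toxicities other than acneiform rash".
- Without improvement: "If acneiform rash does not improve during this time, cetuximab will be permanently discontinued".
- In the next paragraph, participants who have missed more than 2 infusions in a row because of the rash, whose toxicity has resolved and who are thought still to benefit, "may resume cetuximab with Sponsor approval".

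**Cohort A2, Table 11.** Its first column is headed "Dermatologic toxicities and infectious sequelae (eg, acneiform rash, mucocutaneous disease". For a first Grade 3 or 4 event within a cycle, infusions are omitted for 1 to 2 weeks and then: "if condition improves, continue at the same dose of 250 mg/m"² (the squared sign falls outside the quoted run). Dose level 1 enters at the second occurrence and dose level 2 at the third. Without improvement in the within-cycle branch, cetuximab is discontinued. In the Day 1 branch of occurrences 1 to 3, the cycle is delayed until improvement, with no time limit given.

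**Cohort A2, Table 5.** It lists the starting dose and two reduced levels (200 and 150 mg/m²). It contains no rule by grade, occurrence, omission or stopping.

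**Cohort B2, Section 6.5.4.7 with Tables 10 and 4.** The rules are the same under other table numbers. One added sentence says that management of dermatologic toxicities by severity is set out in Table 10.

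**The concern.** Severe rash is an expected cetuximab toxicity, and the Cohort A2 risk section (2.3.1.3) says that SAR444245 could increase cetuximab skin toxicity. The rules should therefore give one answer for each event. As written, an investigator handling a first severe rash finds a sentence ordering a reduction and a table row ordering none. For severe mucocutaneous disease, the text leads to a list of dose levels and the table heading leads to a full algorithm. For a rash still unimproved at two weeks, the text ends cetuximab, while the next paragraph and the Day 1 branch leave room to wait and restart.

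At stake is uneven handling across sites of dose, of the trigger for reduction and of permanent discontinuation of cetuximab. Exposure and discontinuation summaries would then partly reflect which sentence a site followed.

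**Working it through.** The plan states no figure to reproduce on this point. The check compares the instructions side by side, with one conversion from weeks to infusions and one expected count.

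| Situation | Text (A2 6.5.4.5; B2 6.5.4.7) | Table (A2 Table 11; B2 Table 10) |
|---|---|---|
| First Grade 3/4 acneiform rash, improved | Reduce, citing the table | Same dose; reduction starts at the second occurrence |
| Grade 3/4 skin toxicity other than acneiform rash | Table 5 (A2) or Table 4 (B2): dose levels only | Covered by the heading, with mucocutaneous disease named |
| Not improved after 1 to 2 weeks, within a cycle | Discontinue permanently | Discontinue |
| More than 2 infusions in a row omitted for rash | May resume on resolution, with perceived benefit and Sponsor approval | Not addressed |
| Event on Day 1 | Not separately addressed | Delay until improvement; no 1 to 2 week limit |

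**Step 1, dose at first occurrence.** The text makes no exception for a first event, while the row it points to contains no reduction. From the second occurrence, text and table agree, so the conflict is confined to the first.

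**Step 2, which table.** Table 11 takes its dose levels 1 and 2 from Table 5, so the two tables share the same steps. Only Table 11 says when a step is taken. A non-acneiform Grade 3 event therefore has a full algorithm under the table heading and no trigger under the text. In Cohort B2 the contradiction lies inside one section: non-acneiform events go to Table 4, and skin toxicity management as a whole goes to Table 10.

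**Step 3, stopping and resumption.** The schedule is weekly ("followed by weekly 250 mg/m"², protocol synopsis).

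- Omission of 1 to 2 weeks = 1 to 2 infusions.
- More than 2 consecutive infusions = at least 3 infusions = at least 3 weeks.

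The resumption paragraph therefore begins after the point at which an unimproved rash has already ended cetuximab. It can operate only for rashes that improved without resolving, or for some other subset, and the document does not say which. For Day 1 events, the nearest limit is the general one in Section 6.5.2: Sponsor consultation and clear benefit beyond 14 days, and permanent discontinuation beyond 84 days.

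**Step 4, does another rule settle it?** Section 6.5.1 applies the most conservative adjustment when a participant has several toxicities with conflicting recommendations. It does not address two rules for one toxicity. Section 6.5.2 allows restart after 2 to 4 consecutive omissions with clear benefit and Sponsor consultation, which sits beside the rash-specific stopping rule without ranking the two.

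**Step 5, how many participants.** The input is 9.7% Grade 3 or 4 acneiform rash with cetuximab across trials (A2 Section 2.3.1.2 and Table 16; B2 Section 2.3.1.1 and Table 13), with 40 participants planned in A2 and 40 in the B2 core.

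- Expected number per cohort core: 0.097 × 40 = 3.88, about 4.
- Chance of at least one: 1 − (1 − 0.097)^40 = 0.983.
- Range if the true rate were half or double: 0.0485 × 40 = 1.9 and 0.194 × 40 = 7.8.

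**The case against.** Several parts of the case against have weight.

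**The text defers to the table.** It names no dose of its own, and a site that opens Table 11 finds an explicit first-occurrence row. This narrows the dose conflict but does not remove it, because the sentence still orders a reduction that the row does not contain. A reader might infer a gap of 250 against 200 mg/m², or 50/250 = 20% of the weekly dose. The documents do not support that as a fact: 200 mg/m² appears only for the second occurrence, and neither place assigns it to the first.

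**Improvement and resolution differ.** A rash can improve within two weeks and still miss the Grade 1 or baseline level that Section 6.5.2 asks for after a delay, so a third omission need not mean non-improvement. Resumption also carries three conditions: resolution, perceived benefit and Sponsor approval. That is a plausible intended reading, so this part is an unresolved overlap and not a flat reversal. The document never states that scope.

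**Day 1 events.** A reader might infer a further contradiction because the text omits cetuximab alone while the table delays the cycle for all study drugs. That does not hold. Section 6.5.1 separates cycle delay on Day 1 from omission within a cycle, and the table applies that split. Only the missing time limit in the Day 1 branch remains.

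**Investigator discretion.** The tables are headed as recommendations, and Section 6.5.3 leaves the final dose decision to the investigator. Some variation is therefore allowed by design, but that does not justify guidance that disagrees with itself.

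**Conclusion.** The inconsistency is real in the current text of both substudies, in three parts: the dose at first occurrence, the table for non-acneiform toxicity, and the unstated boundary between permanent discontinuation and resumption, including Day 1 events. The second is the clearest clash, the first is confined to first occurrences, and the third is an ambiguity of scope.

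About 4 of 40 participants per cohort core would have a Grade 3 or 4 acneiform rash, assuming that the 9.7% cetuximab rate carries over to these combinations. Not every one of them would meet every conflict, and the count excludes non-acneiform events.

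Stronger conclusions that a reader might draw are not supported:

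- A B2 count on 96 participants assumes that the conditional expansion opens.
- Calling severe rash one of the regimen's most common severe toxicities goes beyond the document, which gives no rates for these combinations and cites Grade 3 and 4 hypomagnesemia at 6% to 17% with cetuximab.
- No effect on the response rate is demonstrated.
- In the A2 safety run-in, the effect on dose-limiting toxicity counts is probably small, because Grade 3 or higher events generally qualify already under Section 4.1.

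The point should be corrected. It does not by itself undermine the design.

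**What to change.** Reconcile Section 6.5.4.5 with Tables 11 and 5 in Cohort A2, and Section 6.5.4.7 with Tables 10 and 4 in Cohort B2, so that:

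1. text and table give the same instruction after a first Grade 3 or 4 occurrence;
2. one table governs skin toxicity other than acneiform rash, and headings and cross-references agree with that;
3. the cases covered by the discontinuation rule and by the resumption paragraph are stated, including events present on Day 1 and the relation to the general limits in Section 6.5.2.

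The clinical team decides the content of each rule; this review takes no view on which is right. The cost is wording in two substudies, with no change to sample size or analysis.
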